3.2 Composition of the data monitoring committee, its role, and reporting structure

This study will be monitored by a data and DSMB of the CTU of the Children's Hospital of Fudan University. The DSMB is independent of the sponsor and has no competing interests in this study. Consisting of independent clinical experts and statisticians, the DSMB reviews the progress and safety of the trial weekly.

3.3 Adverse event reporting and harms

There is no known severe adverse event caused by routine physical exercise or Baduanjin exercise. Study physicians will take care of the common response to exercise, including sore

muscles and fatigue. Unintended effects of trial interventions discovered by study physicians or therapists will be recorded and reported to the principal investigator within 24 hours.

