2.5 Criteria for discontinuing interventions

Participants can leave the trial at any time for any reason without any consequences if they request to do so. If they decide to leave before the intervention starts, the patient will be replaced by the following new patient. During the intervention, the drop-out is defined as the following: changing the dose of methylphenidate and or receiving another behavioral intervention according to the advice of an independent child psychiatrist, stopping taking exercise for two consecutive weeks without a reasonable cause, and/or the refusal to attend both study visits at 3 months \pm 4 weeks and 6 months \pm 4 weeks after allocation. Advises about preventing sports injury are talked about with caregivers at the enrollment. In case of a sports injury or illness for other reasons, the caregivers are asked to contact the primary investigator to discuss whether to pause the exercise or end it. The patient data will be recorded up to the drop-out and included in the analysis.

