2.5.1 Strategies to improve adherence to interventions

In this trial, each family has a Wechat discussion group where they can upload their biological data and contact the researcher conveniently. Researchers will check the uploaded data every

morning and give feedback to caregivers in the discussion group. When the data is not uploaded, researchers will remind the caregivers to upload data and make sure that if they have any difficulty in continuing the exercise. Researchers will also check the data uploaded automatically by the Baduanjin software to ensure the movements were adequately practiced. When unqualified exercise data is identified, the researcher will contact the caregiver to modify their exercise status and guide them to meet the requirement of exercise intensity and movement accuracy.

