2.5.2 Definition of adherence

Researchers will check the uploaded data every day. If the time of exercise exceeds 30 minutes, and the maximum heart rate during the exercise is over 120 beats per minute, it is recorded as a day that meets the adherence standard. For the participants in the Baduanjin group, the score automatically rated by the Baduanjin software should also exceed 77.5. We require the participants to meet the adherence standard for at least 5 days each week. Participants that finished less than 80% required days are defined as having poor adherence.

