### **3.6. Sample Size**

The sample size was calculated based on the primary outcome. According to our 3 months pilot study, the change score of Hyperactivity/Impulsivity assessed by doctor version of SNAP-IV scale in Baduanjin practice group (N=23) was 3.52 with a standard deviation of 5.81. Based on the outpatient data among ADHD patients, the mean change score Hyperactivity/Impulsivity assessed by doctor version of SNAP-IV scale in regular physical exercise patients was 0.37 with a standard deviation of 3.72. We assumed that the difference in the mean change score between Baduanjin practice group and regular

physical exercise group was 3.1 a standard deviation of 5.8. So as to demonstrate superiority with 80% of power and a significance level of 0.05 (two-sided), at least 56 participants for each arm will be required. With an anticipated a drop-out rate of 5%, a total of 120 participants need to be randomized.

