#### *-Safety population*

Participants who were given any exercise-relate-treatment would be included in this population. Adverse reactions and events would be recorded. This population will be used for the supportive analyses.

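### Protocol 3.3 commits to recording only staff-found effects of the interventions, which is narrower than what SAP 4.2 expects, so harms may be under-counted by an unknown amount

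*Protocol*

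**What the plan says.** Protocol 3.3 is the only section on adverse-event reporting. Its recording rule is: "Unintended effects of trial interventions discovered by study physicians or therapists will be recorded and reported to the principal investigator within 24 hours". The sentence before it deals with soreness and fatigue: "Study physicians will take care of the common response to exercise". That is a commitment to care, with no mention of an entry.

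SAP 4.2, under the safety population, is broader: "Adverse reactions and events would be recorded". It names no method and no table. SAP 7 lists AE and AEdetail in both the 3-month and 6-month blocks, ADeal in the 3-month block, and fields for who stopped and why in both. None is tied to an arm or limited to related events. There is no onset-date or relatedness variable.

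Other passages bear on how an event comes to light:

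- Protocol 2.5, which treats injuries during exercise together with "illness for other reasons, the caregivers are asked to contact the primary investigator to discuss whether to pause the exercise or end it".
- Protocol 2.5.1: when data are missing, "researchers will remind the caregivers to upload data and make sure that if they have any difficulty in continuing the exercise".
- Protocol 3.1: the study therapist follows participants daily.
- Protocol 3.2: "the DSMB reviews the progress and safety of the trial weekly".

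**The concern.** The protocol's rule puts two conditions on an entry: study physicians or therapists find the event, and it counts as an effect of the intervention. The safety analysis in the SAP is framed for events in general. If entry follows the protocol, the analysis receives a filtered set of events. An illness or injury judged unrelated need not appear, and soreness or fatigue can be treated without being counted. Without a relatedness variable and the excluded events, nobody could later check how the causal judgement was made.

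At stake is the by-arm harms count, any statement that no harm was seen, and the monitoring board's weekly safety review if it draws on these records. The trial enrols children aged 7 to 16 who exercise at home, so readers will want a harms statement. The primary efficacy comparison does not depend on any of this.

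**Working it through.** **1. The passages side by side.**

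| Source | Events covered | Recording stated? |
|---|---|---|
| Protocol 3.3, unintended effects | Caused by the intervention, found by staff | Yes |
| Protocol 3.3, soreness and fatigue | Common exercise responses | No, care only |
| Protocol 2.5, caregiver contact | Injury, or illness of any cause | No; purpose is to pause or end exercise |
| Protocol 2.5.1, daily data check | Difficulty continuing, when data are missing | No |
| SAP 4.2, safety population | Reactions and events generally | Yes, no method |
| SAP 7, AE fields | Not restricted | Fields exist; no definition or question given |

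Only Protocol 3.3 says which events qualify, and it is narrower than SAP 4.2. No passage gives a standard question. The tables in SAP 6.2 include none for safety, though that section allows further tables.

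**2. Number per arm.** SAP 3.6 states that "a total of 120 participants need to be randomized", allocated 1:1, so 120 / 2 = 60 per arm. The figure behind it reproduces. With difference 3.1, SD 5.8, two-sided 0.05 and 80% power, 2 × (1.960 + 0.842)² × (5.8 / 3.1)² = 55 per arm, or 56 with the t distribution, as stated. Then 112 / 0.95 = 118, and 120 is the next multiple of the block size of 4.

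**3. What zero recorded events would show.** The documents give neither an event rate nor a recording rate, so the recording share r is assumed. Suppose each affected child is recorded independently with probability r.

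One-sided 95% upper limit for the recorded risk with 0 of 60: U = 1 − 0.05^(1/60) = 0.0487. Limit for the true risk: U / r. Chance of recording nothing in an arm when the true risk is 10% (also assumed): (1 − 0.10 × r)^60.

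| r (assumed) | Upper limit, true risk | Chance of zero recorded at 10% true risk |
|---|---|---|
| 1.00 | 4.9% | 0.2% |
| 0.75 | 6.5% | 0.9% |
| 0.50 | 9.7% | 4.6% |
| 0.25 | 19.5% | 21.9% |

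With 56 per arm, the limit at full recording is 5.2%.

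**4. Equal under-recording in both arms.** The recorded difference is r times the true difference. For assumed true risks of 30% and 10%, expected counts are 60 × 0.30 = 18 against 60 × 0.10 = 6 at full recording, 9 against 3 at r = 0.50, and 4.5 against 1.5 at r = 0.25. Equal loss does not create a difference, but it shrinks a real one.

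**The case against.** The strongest reply is that the documents should be read together. Protocol 3.3 does not say that other events go unrecorded. SAP 4.2, in the later document, calls for reactions and events to be recorded, and SAP 7 has general fields at both follow-up visits, next to the scheduled scales. An event that ends participation also has stop-reason fields to hold it. Caregivers are told to report injury or any illness, the therapist is in daily contact, and an event reported by a caregiver can fairly be called discovered by staff. The case report form is not in the documents and may contain a standard question.

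Most of that stands. A reader might infer that harms will be under-counted, or that a harms comparison would be worthless. The documents do not support that: these routes may catch much of what section 3.3 leaves out. The reply does not remove the mismatch, because the fields do not say what qualifies and the one passage that does is the narrow one.

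A reader might also infer a bias between arms, because of an adherence criterion that applies to one arm only: "For the participants in the Baduanjin group, the score automatically rated by the Baduanjin software should also exceed 77.5". A failed score could prompt an extra contact. But the recording rule and the daily contact are the same in both arms, and no difference in capture can be shown.

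It is also fair to say that the recording shares and risks in the working have no source, and that the plan names no between-arm test for harms. The figures illustrate what incomplete recording does; they do not estimate it.

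**Conclusion.** The point holds as a mismatch of scope with a possible consequence. Protocol 3.3 commits to recording a narrower set of events than SAP 4.2 expects. If it is used as the entry rule, events judged unrelated and common exercise responses may be missed.

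The size is unknown. Under assumed recording shares from 100% down to 25%, the upper limit on true risk after zero recorded events in 60 children runs from 4.9% to 19.5%. This takes 60 per arm in the safety population and independent recording with the same share for every child. Until the rule is aligned, a by-arm count or a claim of no harm should say that recording may have been incomplete. It deserves correction because the remedy is cheap; it is no threat to the main result.

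**What to change.** 1. Reword Protocol 3.3 so that all adverse events from allocation to the 6-month visit are recorded in both arms, whatever their presumed cause. Name soreness, fatigue, and any injury or illness that caregivers report under section 2.5.
2. Ask every caregiver one identically worded question at the existing 3- and 6-month visits, and keep the answers from the blinded raters.
3. Keep 24-hour reporting to the principal investigator for unintended effects of the interventions, as now. Do not extend it to every minor event.
4. Add onset date and relatedness to both adverse-event blocks in SAP 7.
5. State in SAP 4.2 that all events are tabulated by arm in the safety population.

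The cost is a few sentences, one form item, two variables per block and more minor events to enter. Two visits for 120 families means at most 240 answers. Weekly questioning for about 13 weeks would mean 13 × 120 = 1,560, which is more than this needs. The price of the lighter schedule is weaker recall of minor complaints.

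Protocol 1.3 plans conduct to March 2022 and SAP 2.0 is dated October 2022. If collection has closed, what remains is the by-arm table and a plain statement of how events were recorded.

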3.4 Frequency and plans for auditing trial conduct

The process will be independently audited by investigators and the sponsor every three months.

3.5 Plans for communicating important protocol amendments to relevant parties (e.g. trial participants, ethical committees)

When a substantial modification is made in the case of significant changes to eligibility criteria, outcomes, or analysis that may impact the scientific value of the research or the safety or quality of the intervention, it will be notified to the CTU and the competent authority. Minor revisions of the protocol will be recorded and reported to the CTU. Participants will be informed about the eligibility criteria or intervention changes. Additional consent forms will be signed and filed if needed.

## SAP version history

**Chief investigator:** Phd [name]

**Trial statisticians:** [name]; Phd [name]

**SAP authors:** [name]; [name]; [name]; [name]

Version Date	SAP version#	Details of Changes	Signatures
September 27, 2021	1.0	-	-
December 8, 2021	1.2	Adding detail description of multiple imputations	[name] [name] [name]
December 12, 2021	1.3	Add Graphical/Table displays	[name] [name] [name]
July 26, 2022	1.4	Adding more secondary outcomes (CANTAB test and BRIEF2 scale) analyses; Adding effect size description	[name] [name] [name]
October 25, 2022	2.0	Adding more detail information of sample size calculation ; Adding detail description of GLMM estimation	[name] [name] [name]

Protocol A Randomized Clinical Trial of BaDuanJin in Treatment of Attention Deficit Hyperactivity Disorder with Hyperactive-Impulsive Symptom

# Introduction

ADHD is a common neurodevelopmental disorder characterized by a persistent pattern of inattention and/or hyperactivity and impulsivity, resulting in functional impairment in multiple settings. The prevalence in China is estimated to be 6.26%[1]. Physical exercise is indicated as an alternative approach to the treatment of ADHD, used independently or complementary to medication or behavioral interventions that can yield both acute and lasting positive effects on executive function, which is known as the core neurobiological deficit in ADHD. Baduanjin exercise, a combination of physical exercise and Chinese qigong movement, is considered as a potential alternative treatment to ADHD in Traditional Chinese Medicine (TCM). This study aims to evaluate the effectiveness of Baduanjin exercise on reducing the hyperactive-impulsive symptoms of children with ADHD compared with the current treatment, routine exercise, as the control treatment.

## 1. Study Objective and Outcomes

### 1.1. Study Objective

The aim of this randomized controlled trial is to explore the effectiveness of Baduanjin practice versus routine physical exercise in improving Hyperactive-Impulsive Symptoms among pediatric ADHD patients.

### 2.2. Outcomes

#### 2.2.1. Primary outcome

Hyperactivity/Impulsivity score change assessed by doctor version of SNAP-IV scale at 3th month.

Time Frame: Baseline, 3th month after initiation of intervention

Type: repeated measured continuous variable

### **2.2.2. Secondary outcomes**

(1) Hyperactivity/Impulsivity score change assessed by doctor version of SNAP-IV scale at 6th month.

Time Frame: Baseline, 6th month after initiation of intervention

Type: repeated measured continuous variable

(2) Hyperactivity/Impulsivity score changes assessed by parent version of SNAP-IV scale.

Time Frame: Baseline, 3th month and 6th month after initiation of intervention

Type: repeated measured continuous variable

(3) Changes of Scoring evaluation of the TCM symptoms.

Time Frame: Baseline, 3th month and 6th month after initiation of intervention

Type: repeated measured continuous variable

(4) Change scores of inattention and Oppositional Defiant Disorder (ODD) subscale assessed by doctor version of SNAP-IV scale.

Time Frame: Baseline, 3th month and 6th month after initiation of intervention

Type: repeated measured continuous variable

(5) Change scores of inattention and Oppositional Defiant Disorder (ODD) subscale score assessed by parent version of SNAP-IV scale.

Time Frame: Baseline, 3th month and 6th month after initiation of intervention

Type: repeated measured continuous variable

(6) The changes of Weiss Functional Impairment Rating Scale (WFIRS) score.

Time Frame: Baseline, 3th month and 6th month after initiation of intervention

Type: repeated measured continuous variable

(7) The changes of parent version of Achenbach Child Behavior Checklist (CBCL) score.

Time Frame: Baseline, 3th month and 6th month after initiation of intervention

Type: repeated measured continuous variable

(8) The changes of Child version of Achenbach Child Behavior Checklist (CBCL) score.

Time Frame: Baseline, 3th month and 6th month after initiation of intervention

Type: repeated measured continuous variable

(9) The changes of CANTAB test (neuropsychological tests) score.

Time Frame: Baseline, 3th month and 6th month after initiation of intervention

Type: repeated measured continuous variable

(10) The changes of BRIEF2 scale (ecological rating scale) score.

Time Frame: Baseline, 3th month and 6th month after initiation of intervention

Type: repeated measured continuous variable

(11) The changes of Visual Perception-2nd edition (DTVP-2) score.

Time Frame: Baseline, 3th month and 6th month after initiation of intervention

Type: repeated measured continuous variable

(12) The changes of Child Sensory Integration Checklist score.

Time Frame: Baseline, 3th month and 6th month after initiation of intervention

Type: repeated measured continuous variable

## 3. Study Design

### 3.1. Design

The trial is a single-blind, superiority, randomized controlled trial. Patients fulfil the eligibility criteria as outlined in the protocol are invited to participate consecutively and are randomized individually to control or experimental arm. Block randomization (block size of 4) will be applied.

## 3.2. Trial Sites

Single center: Children's hospital of Fudan University

Children's Hospital of Fudan University is a comprehensive tertiary pediatric hospital and one of the national children's medical centers. Patients are enlisted at the clinic of both Child psychology department and TCM department.

## 3.3. Interventions

### 3.3.1. Experimental group

Intervention: Baduanjin exercise

Use the Baduanjin training system to practice the whole set of Baduanjin at least once a day and at least 5 days each week and last for 3 months.

More detailed information of Baduanjin practice is presented in the protocol.

### 3.3.2. Control group

Active Comparator: Regular physical exercise

Take routine physical exercise (any kind of routine physical exercise including jogging, bike-riding, badminton, table tennis, soccer, basketball, aerobics and rope skipping.) for 30 minutes, 5 days each week under the supervision of caregivers in addition to regular physical activities at school and last for 3 months.

## 3.4. Randomization

According to the random seeds (seed:20200618), numbers from 1 to 6 were randomly generated by the R software (version 4.0.0) for each block, and each number corresponded to one of six plans for allocating four participants of the block to two arms in a 1:1 ratio. Each allocation sequence was placed in small, opaque, and sealed envelopes numbered and marked in order from one to four and were enclosed in a larger,

opaque, and sealed envelope marked with the block number.

A randomization plan and concealed envelopes were prepared by an independent team of statisticians from the Clinical Trial Unit (CTU) of the Children's Hospital of Fudan University. Recruited patients will be randomly allocated in a 1:1 ratio to the control or experimental group based on the randomization plan: After obtaining signed informed consent from the eligible participant, the trained physician will meet with the prespecified institutional nurse to achieve the allocation plan for the very participant, as indicated by the corresponding envelope. Block envelopes and the four enclosed small envelopes will be opened in order. The nurse will administer the allocation record form in front of the physician.

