1.3 Trial design

This is a single-center, single-blind, superiority, randomized controlled trial. This study is planned to be conducted from October 2020 to March 2022 at the Children's Hospital of Fudan University. Patients will be recruited at the child psychology clinic and TCM clinic of the Children's Hospital of Fudan University. Each participant who fulfills the eligibility criteria outlined in the protocol is randomly allocated consecutively to either the Baduanjin exercise group or the general physical exercise group with a ratio of 1:1.

2 Methods: Participants, interventions, and outcomes

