2.3 Who will take informed consent?

This trial's information is posted in our clinic's hallway and introduced to all the families. All the families receiving this information are welcome to sign up for the trial by completing a simple electric application form on their mobile phones. We will screen their application to assess their eligibility and call the parent to provide initial study information and answer their questions. After this discussion, the family intent to participate in the study will be scheduled to meet with the research physician to discuss any remaining questions, finish the inclusion evaluation and sign in the informed consent. Written informed consent is obtained from the legal guardian of each participant before they undergo any interventions related to the study. Researchers will also explain the trial details explicitly to participants over eight years old and obtain their signed consent.

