2.10 Assignment of interventions: allocation

2.10.1 Sequence generation

Recruited patients will be randomly assigned in a 1:1 ratio to the control group or the experimental group through blocked randomization. The randomization sequence is created by the center using SAS (version 9.4) with a block size of 4. An independent statistician will generate the randomization list. A sequence of subjects' IDs and intervention allocations was generated by creating a random variable and ordering that variable.

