2.10.2 Concealment mechanism

The statistician will conceal the allocation sequence and place it sequentially numbered, opaque, sealed, and stapled envelopes. After signing the informed consent from parents, the study investigators will open the envelopes in consecutive orders and randomly assign the subjects to the intervention group or the control group according to the allocation scheme in the envelope.

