2.10.3 Implementation

The statistical department of our hospital generates the allocation sequence. The researchers will use the prepared sealed envelopes to allocate the patient to a study arm and finish the enrollment procedures. The study group will be revealed, and intervention will be introduced after allocation to the participants.

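### Baseline doctor-rated H/I is a covariate in no planned analysis, and printed blocks of 4 make some allocations predictable to anyone who knows the earlier ones

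*SAP*

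**What the plan says.** **Baseline score.** Protocol 2.2.1 requires a doctor-rated H/I score of at least 12. Protocol 2.6.1 defines the primary outcome as the 3-month score minus the baseline score on the same scale. The model in SAP 5.1.1 has treatment, time, their interaction and a random effect for the child. SAP 5.1.3 adds seven covariates: sex, height, weight, age, IQ, prior exercise time and medication use. Baseline H/I is not among them. SAP 5.1.4 uses a categorized baseline SNAP score only to form subgroups, if these are large enough.

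**Allocation.** Protocol 2.10.1: "The randomization sequence is created by the center using SAS (version 9.4) with a block size of 4". SAP 3.1: "Block randomization (block size of 4) will be applied". SAP 3.4 instead has R drawing one of six plans per block, with four numbered envelopes inside a block-numbered one: "Block envelopes and the four enclosed small envelopes will be opened in order". There, "the trained physician will meet with the prespecified institutional nurse to achieve the allocation plan", and the nurse completes the record while the physician watches. In Protocol 2.10.2, "the study investigators will open the envelopes in consecutive orders". Protocol 2.10.3 adds: "The study group will be revealed, and intervention will be introduced after allocation to the participants".

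**Recruitment.** Under Protocol 2.3 a family is "scheduled to meet with the research physician to discuss any remaining questions, finish the inclusion evaluation and sign in the informed consent". Protocol 3.1 gives the study physician both the finding of recruits and the taking of consent.

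**Safeguards.** Envelopes are opaque, sealed, prepared by statisticians and opened after consent. Protocol 1.3 says each eligible child "is randomly allocated consecutively to either the Baduanjin exercise group or the general physical exercise group". Under Protocol 2.11.1 a psychiatrist unaware of allocation rates SNAP-IV. Protocol 2.11.1 and SAP 3.5 say that the study team receives the allocation only after database lock.

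**Timing.** Table 1 (Protocol 2.7) puts enrolment two weeks before allocation. Protocol 2.4.2 has Baduanjin families receiving their equipment on the enrolment day, and Protocol 2.6.1 equates three months from enrolment with three months of intervention.

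**The concern.** With a known block size and visible block boundaries, anyone who has seen enough of a block knows what remains in it. Opaque envelopes hide their contents but do not prevent that deduction. If the next arm can be foreseen while inclusion is still being decided, the children entered can differ by arm, and blinded rating afterwards does not undo it.

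The most direct place for such a difference to appear is baseline doctor-rated H/I, which sets eligibility and enters the primary outcome. The plan would display an imbalance (SAP Table 1A) and might stratify by it (SAP 5.1.4), but no analysis gives an overall treatment effect adjusted for it. The same gap applies to an imbalance that arises by chance.

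**Working it through.** **1. The plan's own figures.** With a difference of 3.1, SD 5.8, two-sided 5% and 80% power (SAP 3.6), n per arm = 2 × [5.8 × (1.960 + 0.842) / 3.1]² = 54.95; the t-based value is 55.93, so 56 as stated. Then 112 / 0.95 = 117.9, or 118, and the next multiple of 4 is 120, which is 30 blocks. C(4,2) = 6 matches the six plans in SAP 3.4. The documents give no predictability figure.

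**2. Predictability.** This enumerates the six plans for someone who knows every allocation made so far. A queued child is one accepted but not yet allocated when the next inclusion is decided.

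| Queued ahead | Certain, positions 1 to 4 | Mean | Correct guess, positions 1 to 4 | Mean |
|---|---|---|---|---|
| 0 | 0, 0, 1/3, 1 | 33.3% | 1/2, 2/3, 2/3, 1 | 70.8% |
| 1 | 0, 0, 0, 1/3 | 8.3% | 1/2, 1/2, 2/3, 2/3 | 58.3% |
| 2 | 0, 0, 0, 0 | 0% | 1/2, 1/2, 1/2, 2/3 | 54.2% |
| 3 or more | 0, 0, 0, 0 | 0% | all 1/2 | 50.0% |

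With no queue, the certain count over 30 blocks is 30 + Binomial(30, 1/3): mean 40 of 120, central 95% range 35 to 45. If each earlier allocation is seen only with probability 0.5 (assumption), 8.3% are certain and 59.9% are guessed correctly.

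**3. Effect of a two-week gap.** Assume 120 children accrue evenly over 18 months (the whole period in Protocol 1.3) or over 12 months (leaving six for follow-up). Arrivals in 14 days are 120 × 14/547 = 3.1 or 120 × 14/365 = 4.6. With Poisson arrivals of mean m, the certain share is e^(−m) × (1/3 + m/12).

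- m = 3.1: 0.0450 × (0.333 + 0.258) = 2.7%.
- m = 4.6: 0.01005 × (0.333 + 0.383) = 0.7%.

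**4. What an unadjusted contrast carries.** Let D be the baseline difference between arms, r the correlation of baseline with 3-month score, and k the baseline SD divided by the 3-month SD. The slope of the 3-month score on baseline is r/k.

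- The change-score contrast carries (r/k − 1) × D, which is zero only if r = k.
- A raw 3-month contrast carries (r/k) × D.

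With k = 1 and D = 1 point, the change-score contrast shifts by −0.7, −0.5 or −0.3 points at r = 0.3, 0.5 or 0.7. This is the shift per point of imbalance, not an estimate of D.

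**5. Precision cost of adjustment.** The large-sample variance of the adjusted effect relative to the change-score effect is (1 − r²) / (k² + 1 − 2rk). Assume r from 0.3 to 0.7 and k from 0.6 to 1.0.

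- r = 0.3, k = 1: 0.91/1.40 = 0.65, the minimum.
- r = k = 0.7: 0.51/0.51 = 1.00, the maximum, reached wherever r = k.

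**The case against.** A reader might infer that recruiters could foresee a third of the allocations. The documents do not support that. The figure needs one person who knows every earlier allocation and has no queue. The research physician, the study physician and the trained physician may be different people, recruitment runs through two clinics, and two passages say the study team learns the allocation only after lock. That last statement conflicts with Protocol 2.10.2 and 2.10.3 and SAP 3.4, but it cannot simply be ignored. Families apply themselves online, and if the blinded psychiatrist also rates baseline, a recruiter could influence who enters but not the score.

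A reader might also infer same-day allocation. Protocol 2.10.3 lets enrolment procedures finish at allocation, so the equipment passage need not contradict Table 1. Follow-up is elsewhere counted from allocation with a window of plus or minus four weeks, so the enrolment wording in Protocol 2.6.1 may be loose. The passages pull in different directions without settling the matter.

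Finally, baseline is not ignored: it is subtracted, or it sits in the outcome vector if raw scores are modelled. Neither is covariate adjustment (step 4), and the SAP does not say clearly which applies.

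These objections remove any claim of actual selection. They leave the missing covariate and the conflicting passages in place.

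**Conclusion.** The point stands as a should-fix gap in the analysis, made more relevant by the randomization design. Baseline doctor-rated H/I is a covariate in neither the primary nor the adjusted analysis, and the subgroup analysis does not replace it.

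The 33.3% and 70.8% figures are exact but conditional on full knowledge and no queue. They are an upper case, not a description of what happened. If the two-week gap is real, certain predictions are rare: about 0.7% to 2.7% under the assumed Poisson accrual. The documents establish neither full knowledge nor same-day allocation, and they show no breach. The size of any bias cannot be derived from them.

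**What to change.** 1. In SAP 5.1.3, add an analysis of the 3-month doctor-rated H/I change with baseline doctor-rated H/I (`DSNAP_HYP`, already in the SAP 7 variable list) as a covariate. State in SAP 5.1.1 whether the response is the change or the raw score. If raw scores including baseline are modelled, constrain the arms to a common baseline mean instead. Label the analysis post hoc if it is added after database lock. The cost is one short analysis with no patient burden and no meaningful loss of precision. It does not correct selection on unmeasured traits.

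2. Reconcile four sets of passages and state what was done. Report the actual days from inclusion evaluation to allocation. The cost is wording.
   - List generation: Protocol 2.10.1 (SAS) and SAP 3.4 (R).
   - Envelope opening: Protocol 2.10.2 and SAP 3.4.
   - Who learns the allocation: Protocol 2.10.2, 2.10.3 and SAP 3.4, against Protocol 2.11.1 and SAP 3.5.
   - Timing: Protocol 2.4.2 and 2.6.1, against Table 1.

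3. Optional: a Berger-Exner-type check. From the allocation record, compute each child's predicted probability of Baduanjin, (2 − Baduanjin places used in the block) / (4 − places used). Regress baseline H/I on it and report the slope with its 95% CI. In simulations at n = 120, power was 78.7% for a shift of 0.85 SD across the 0 to 1 range, 83.9% for 0.9 SD, and 81.3% for 0.95 SD confined to certain slots. State that a null result is therefore not proof.

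Changing the block sizes is not proposed. SAP version 2.0 is dated October 2022 and the trial was planned to end in March 2022, so the change is very probably moot.
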